1. INTRODUCTION

1.1. Background

Varicella-Zoster Virus (VZV) causes two distinct diseases. Varicella (chickenpox) occurs shortly after primary VZV infection and is characterized by systemic illness and a widely disseminated rash. HZ (shingles) occurs when VZV reactivates from latency. Vaccination as a means to reduce risk of HZ has been examined in both older and immunocompromised persons.

HZ is characterized by rash, and pain/or pruritus. The typical HZ rash, vesicles in a localized, dermatomal band on one side of the body, lasts 2 to 4 weeks and is often accompanied by severe pain that is described as burning, shooting, or stabbing. In some patients, even lightly touching the affected area may cause pain, a phenomenon known as allodynia. Pruritus, which can also be severe, may be as common as pain. Pain that persists after the resolution of the HZ rash is called postherpetic neuralgia (PHN). Notably, PHN can last for months or even years.

Half of all HZ cases occur in individuals \geq 60 years of age (YOA). Individuals who reach 85 years old have a 50% chance of having HZ during their lifetime [Oxman, 2005]. The risk for PHN is also highest in older people with HZ, occurring in 18-50% of those \geq 70 YOA [Oxman, 2005; Scott, 2006; Dworkin, 2007]. Since the loss of VZV-specific T-cell responses as a result of aging leads to heightened susceptibility to HZ, vaccination is considered as a means to reduce the risk of HZ in older adults [Oxman, 2005; Sperber, 1992].

Associated with HZ and its complications is a substantial negative impact on patients' Quality of Life (QoL) and their ability to engage in Activities of Daily Living (ADL). In addition to the morbidity encountered by the individual with HZ, including productivity loss, it can also have significant consequences for the caregiver(s) of patients including partners and relatives of people with HZ [Gater, 2015]. Acute HZ and HZ-related complications such as PHN have a considerable economic cost to healthcare systems caring for HZ and PHN patients. These healthcare costs will most likely increase due to the aging population, where age-related diseases such as HZ are becoming a growing economic burden in the developing world [Szucs, 2013].

A live attenuated VZV vaccine, *Zostavax* (Merck & Co), is licensed in the United States (US) to prevent HZ in persons \geq 50 YOA [*Zostavax* Prescribing Information, 2011]. Live attenuated vaccine is contraindicated in immunosuppressed or immunodeficient individuals [Kroger, 2011].

GlaxoSmithKline (GSK) Biologicals' HZ candidate vaccine is an adjuvanted recombinant VZV envelope glycoprotein E (gE) subunit vaccine, hereafter referred to as HZ/su. The antigen component of the study vaccine is a truncated form of gE. The adjuvant is AS01_B, which consists of liposomes in combination with 50 μ g 3-O-desyl-4'-Monophosphoryl Lipid A (MPL) and 50 μ g *Quillaja saponaria*, Molina, fraction 21

(purified natural saponin molecule extracted from the South American tree, *Quillaja saponaria*) (QS21) per 0.5 mL dose.

The GSK Biologicals' HZ/su candidate vaccine has been evaluated in several studies in healthy and immunocompromised adults. In these studies it elicited strong cellular and humoral immune responses. Furthermore, the safety and reactogenicity profile of the candidate vaccine was acceptable.

Two large pivotal phase III trials ZOE-50 (ZOSTER-006) and ZOE-70 (ZOSTER-022) that enrolled subjects ≥ 50 and ≥ 70 YOA, respectively, evaluated the vaccine efficacy, immunogenicity and safety of GSK Biologicals' HZ/su vaccine. These randomized trials together enrolled more than 30,000 subjects who either received the HZ/su vaccine or placebo on a 0, 2-month schedule.

The final analysis of the ZOSTER-006 primary efficacy objective (Q4 2014) demonstrated that the vaccine is highly efficacious in adults ≥ 50 YOA, with efficacy against HZ of 97.2% (95% confidence interval (CI) of 93.7-99.0). In addition, efficacy against HZ was between 96.6% and 97.9% for all pre-specified age groups (50-59, 60-69 and ≥ 70 YOA) [Lal, 2015]. The results from ZOSTER-022 indicated that the primary objectives have also been successfully met, demonstrating 89.8% (95% CI of 84.2-93.7) efficacy against HZ in subjects ≥ 70 YOA and are therefore consistent with the results of ZOSTER-006. In addition, the first primary objective of pre-specified pooled analysis of ZOSTER-006 and ZOSTER-022 demonstrated that HZ/su effectively prevents PHN. HZ/su was demonstrated to be 88.8% (95% CI of 68.7-97.1) efficacious in preventing PHN in people ≥ 70 YOA. No safety concerns have been raised.

Please refer to the current Investigator Brochure (IB) for information regarding the pre-clinical and clinical studies of HZ/su vaccine.

1.2. Rationale for the study and study design

1.2.1. Rationale for the study

Nearly 22,900 subjects received the active HZ/su study vaccine in clinical trials worldwide, most of whom (95%) were ≥ 50 YOA. Due to the high efficacy of the vaccine, most HZ and PHN cases were prevented, thus avoiding any negative impact on QoL in those subjects. No imbalance between the vaccine and the placebo arms were found in terms of SAEs, potential Immune-Mediated Diseases (pIMDs) or death during the entire duration of the studies. The vaccine was generally well tolerated. However, the vaccine was more reactogenic than placebo (saline solution).

In the pooled analysis of the ZOSTER-006 and ZOSTER-022 studies the most common side effects were at the site of injection, including pain, redness, and swelling. Up to 70% of people who received the HZ/su vaccine had pain at the injection site. These symptoms were usually mild and resolved within about 3 days on average. The incidence of grade 3 solicited local pain, was about 4%, with an average duration of less than 2 days. Grade 3 reactogenicity is defined as preventing ADL. Other side effects seen in more than 10% of people who received the vaccine included myalgia, fatigue, headache, shivering, fever

and gastrointestinal symptoms such as nausea, vomiting, diarrhoea and/or abdominal pain. The incidence of myalgia and fatigue was about 33% (overall/dose) and had an average duration of 2.5 days. The incidence of grade 3 solicited general symptoms was 3% or less (overall/dose) with average durations of less than 2 days. The reactogenicity is likely to be secondary to the enhanced innate immune responses elicited at the site of injection and therefore is expected [Didierlaurent, 2014]. This is consistently observed in studies evaluating AS01 – (and other) adjuvanted vaccines, in which higher reactogenicity is observed with adjuvanted versus non-adjuvanted vaccines [Stassijns, 2016].

While grade 3 reactogenicity is defined as preventing ADL, there is no clear understanding available on how this translates to impact on the daily Physical Functioning (PF) of an individual. As such this study is designed to quantify the impact of reactogenicity in terms of PF (e.g., walking, carrying groceries, climbing stairs, etc.). In addition, the Quality-adjusted life year (QALY) loss associated for both *Zostavax*-vaccinated and non-vaccinated subjects with a HZ case that did not lead to PHN, has been estimated to be approximately 0.01 (i.e., 3.65 days) [Pellissier, 2007]. For HZ cases that led to PHN, it was between 38.69 and 56.94 days, resulting in QALY losses of 0.106–0.156 depending on age for non-vaccinated subjects, [Pellissier, 2007]. Similar results were observed in the ZOSTER-006 and ZOSTER-022 studies with the HZ/su vaccine. As such, QALY loss can be avoided by preventing HZ and PHN, through HZ/su vaccination. However reductions in QALY loss by preventing HZ and PHN through HZ/su administration could be partially offset by the QALY loss related to reactogenicity that is associated with vaccination.

In assessing the impact on QoL, the QALY loss due to adverse events is an important parameter to include when calculating the cost/effectiveness of HZ/su compared to no vaccination. These data will be included in models which analyze net QALY loss avoided by preventing HZ and PHN by vaccinating with HZ/su. Furthermore, only limited data are available to assess the impact of the reactogenicity on the Quality of Life (QoL) and PF of individuals exposed to the HZ/su vaccine or vaccination in general. These data are important to both Health Care Providers (HCPs) and policy makers. Additional characterization of the reactogenicity will allow vaccinators to better inform vaccinees before the administration of the vaccine. Therefore, this study will be conducted to enhance our understanding of HZ/su vaccine reactogenicity, and to provide more complete information to vaccinators and persons who will receive the vaccine.

1.2.2. Rationale for the study design

The impact on QoL and QALY loss due to the reactogenicity will be compared to the impact on QoL or QALY loss due to HZ and its complications, notably PHN. This information will be used to better assess the public health impact of HZ/su. For this purpose, SF-36 [APPENDIX A] and EQ-5D [APPENDIX B] questionnaires – the same questionnaires used in the ZOSTER-006 and ZOSTER-022 studies to measure the impact of HZ and PHN on QoL – will be collected during this study.

The study will estimate changes in QoL or QALY loss within the same subjects between before and after HZ/su vaccination, and therefore a placebo control will not be included. (Amended 16 November 2016)

Subjects in the general population (especially older adults), are on average unable to achieve perfect QoL scores, because many subjects may be somewhat limited in “climbing several flights of stairs” or “bending, kneeling, or stooping”. To estimate the impact of reactogenicity on an individual’s SF-36 PF and QoL, we will compare two periods, i.e., pre-vaccination and post-vaccination. The difference is considered to be the effect of vaccination and reactogenicity on the SF-36 PF and QoL. To characterize the study population and determine if frailty may influence reactogenicity and consequently the impact on QoL scores, the subjects’ frailty status will be assessed at inclusion (see Section 10.6.2.2).

In addition to the SF-36 and EQ-5D questionnaires, a more complete characterization of the reactogenicity of the vaccine will be achieved by including a detailed collection of the use of healthcare resources and the occurrence of symptoms through diary card data collection (see Section 5.3.1.1). Impact on days of work loss, both for the subject or for a caregiver, as applicable, will be assessed.

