5.2.2.2.1. Study group and treatment number allocation

The target will be to enrol approximately 400 eligible subjects aged ≥ 50 years.

The enrolment will be performed to ensure equal distribution of the population across the three age strata (50-59 YOA versus 60-69 YOA versus ≥ 70 YOA). Therefore the expected distribution of subjects is as shown in [Table 4](#).

Table 4 Number of subjects required for enrolment

Age strata	Sample size
50-59 YOA	≈ 134
60-69 YOA	≈ 133
≥ 70 YOA	≈ 133
All	≈ 400

The subject will be entered into the applicable age stratum (50-59 YOA versus 60-69 YOA versus ≥ 70 YOA) in SBIR at the investigator site.

After obtaining the signed and dated ICF from the subject and having checked the eligibility of the subject, the study staff in charge of the vaccine administration will access SBIR. Upon providing the age (50-59 YOA versus 60-69 YOA versus ≥ 70 YOA) and the subject identification number, the randomization system will provide the treatment number to be used for the first dose.

The number of each administered treatment must be recorded in the eCRF on the Vaccine Administration screen.

When SBIR is not available, please refer to the SBIR user guide or the Study Procedures Manual (SPM) for specific instructions.

Note that as soon as the target number of subjects in a specific age group has been reached, the enrolment will be frozen for this age group.

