10.6.2. Quality of life

The analysis of QoL will be based on the TVc. An analysis of the impact on reactogenicity and QoL of frailty status will be performed if data allows (see Section 10.6.2.2). Details of this sub-analysis will be elaborated upon in the SAP.

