**Table 1 Details of subgroups**

Sub-group category	Sub-group order in tables	Sub-group label in tables	Sub-group definition for footnote
Age	1	50-59 YOA	50-59 year old subjects
	2	60-69 YOA	60-69 year old subjects
	3	≥ 70 YOA	≥ 70 year old subjects
Frailty Index (FI)	1	Non-Frail	Subjects with frailty index <=3 are considered as Non frail
	2	Pre-Frail	Subjects with frailty index >3 and <=8 are considered as pre fail
	3	Frail	Subjects with frailty index >8 are considered as frail
Maximum Intensity / Reactogenicity Grade	1	Grade 0	Subjects with no solicited symptoms reported.
	2	Grade 1,2	Subjects with at least one grade 1 or 2 (=mild or moderate) solicited AE reported as maximum intensity.
	3	Grade 3	Subjects with at least one grade 3 (=Severe) solicited AE reported as maximum intensity.
Type of Symptom*	1	None	Subjects with no solicited symptom reported
	2	Local	Subjects with at least one solicited local symptom reported
	3	General	Subjects with at least one solicited general symptom reported
Gender	1	Male	Male Subjects
	2	Female	Female Subjects

\*Note that a subject can be included in both Local or General categories

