### 6.2.1. SF-36 and EQ-5D

The SF-36 health survey and the EQ-5D questionnaires will be completed by all subjects at each study visits (i.e., Visit 1 Day -7, Visit 2 Month 0 (before the vaccination), Visit 3 Day 7, Visit 4 Month 2 (before the vaccination) and Visit 5 Day 67). Additionally, after each vaccination, the subjects will be given the questionnaires to take home and asked to complete only questions 3a through 3j of the SF-36 questionnaires and the entire EQ-5D questionnaires, on a daily basis on Days 1 to 6 post-vaccination.

Each of the 8 components of the SF-36 Questionnaire and the EQ-5D Utility and VAS scores will be presented at each scheduled visit (Day -7, Day 0, Day 7, Day 60 and Day 67) including the derived baseline values for each dose. In addition the SF-36 physical functioning score (PF) (based on questions 3a to 3j) and the EQ-5D utility and VAS scores will be presented on days 1 to 6 following each dose. Further details of the SF-36 components and EQ-5D Utility and VAS scores can be found in section [7.1.3](#).

The primary endpoint variable is the SF-36 Physical Functioning (PF) scale. The analysis will be performed on the subgroups detailed in [Table 1](#).

The 10 individual questions that form the SF-36 PF scale will be analysed on an individual basis. The three responses (Limited a lot, Limited a little, Not limited at all) to the individual questions will be assigned a score of 0, 50, or 100. In this way a baseline score and a mean score over the 7 days post each dose can be calculated for each individual question. Summary statistics of the change from baseline will be presented for each individual question.

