## 6.2.2. EQ-5D Utility / Quality adjusted life years (QALY)

The calculation of the baseline and post baseline values for the analysis of QALY loss is detailed in section [7.1.3](#).

The 95% CI for Quality-adjusted life year (QALY) mean loss will be obtained using a multiple regression model on the change from baseline EQ-5D utility scores. The model will include age strata, gender and frailty status as the fixed effect.

The 95% CI for utility scores will be obtained pre- and post-vaccination separately assuming that utility scores were normally distributed with unknown variance.

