## 6.6. Analysis of safety

The primary analysis for safety will be based on the TVC. If the percentage of the vaccinated subjects excluded from the ATP cohort for safety is more than 5%, a second analysis based on the ATP cohort for safety will be performed.

Safety analyses will be performed by age stratum and frailty status (sub-groups are defined in [Table 1](#)).

When appropriate, tabulations will be presented overall and by time of occurrence relative to last vaccination (e.g., using windows such as Days 0 – 6, Days 0 – 29 and more than 30 days post-vaccination).

The following analyses will be performed for safety endpoints:

- The percentage of subjects with at least one local solicited AE, with at least one general solicited AE and with any solicited AE during the solicited 7-day follow-up period will be tabulated with exact 95% CI after each vaccine dose and overall. The same tabulation will be performed for grade 3; related and grade 3 related AEs;
- The percentage of subjects with at least one local AE (solicited and unsolicited), with at least one general adverse event (solicited and unsolicited) and with any AE during the solicited 7-day follow-up period will be tabulated with exact 95% CI after each vaccine dose and overall. The same tabulation will be performed for grade 3, related and grade 3 related AEs;
- The percentage of subjects reporting each individual general AE collected during the pre-vaccination period (Day -7 and Day 0 visits) will be tabulated with exact 95% CI.
- The percentage of subjects reporting each individual solicited local and general AE during the solicited 7-day-follow-up period will be tabulated with exact 95% CI. For all solicited symptoms, the same tabulation will be performed for grade 3 solicited AEs and for solicited general AEs with relationship to vaccination;
- Summary of temperature value by half degree increment reported during the 7-day (Days 0-6) post-vaccination period following each dose and overall doses and subjects. The same tabulation for fever with relationship to vaccination will be done;

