## 9. CHANGES FROM PLANNED ANALYSES

- pIMDs will be described in detail. Sub-groups analyses by age stratum and by frailty status have been added.
- Additional analyses of safety have been added following remarks made by CBER on the Zoster-032 study.

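### Frailty splits of PF change and solicited symptoms are not adjusted for age, although the plan already has an age-adjusted frailty model for QALY loss

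*Protocol*

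**What the plan says.** **The aim.** Protocol 1.2.2 gives two reasons for assessing frailty at inclusion: to characterise the population and to "determine if frailty may influence reactogenicity and consequently the impact on QoL scores". Protocol 10.6.2 adds: "An analysis of the impact on reactogenicity and QoL of frailty status will be performed if data allows". It leaves the detail to the SAP.

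**PF change.** SAP 6.2.1 names SF-36 PF as the primary variable and says "The analysis will be performed on the subgroups detailed in" Table 1. That table lists age, frailty index, reactogenicity grade, symptom type and gender as separate categories. Frailty has three classes defined by the index alone; for the top one, "Subjects with frailty index >8 are considered as frail". No category is crossed with another, and no model for PF change is given.

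**Solicited symptoms.** SAP 6.6 says "Safety analyses will be performed by age stratum and frailty status (sub-groups are defined in" Table 1) and describes percentages with exact confidence intervals. SAP 9 says "Sub-groups analyses by age stratum and by frailty status have been added".

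**QALY loss.** This is the only outcome with a joint model. SAP 6.2.2: "The model will include age strata, gender and frailty status as the fixed effect". SAP 7.1.3.4 gives the code, a linear model with `agecat`, `frail` and `gender`.

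**Age mix.** Protocol 5.2.2.2.1: "The enrolment will be performed to ensure equal distribution of the population across the three age strata", with about 134, 133 and 133 subjects. SAP 6.3 describes the disease list in the frailty index as age dependent; medical history supplies 14 of the 36 possible points.

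**The concern.** Whether frailty influences an outcome is a comparative question. If the frailty classes differ in age, a one-way frailty table mixes the two factors. Age varies widely here by design and the index partly counts age-related disease, so the Frail and Pre-Frail rows will probably be older than the Non-Frail row.

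The frailty rows for PF change or symptom rates could then show a gradient that is only age. They could also hide a real frailty effect if younger subjects react more. A further risk is inconsistency: the QALY frailty result holds age strata and gender fixed and the PF frailty result does not, so the two could disagree for that reason alone. Protocol 1.2.1 intends the reactogenicity data to inform vaccinators and vaccinees, so a misread frailty gradient could reach them.

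**Working it through.** **Plan's own figure.** Protocol 10.3 assumes an SD of 21.2 for PF change and claims a precision of 2.2 with 360 evaluable subjects. Taking a two-sided 95% interval (the level is not stated there), 1.96 × 21.2 / √360 = 2.19. With 10% non-evaluable, 360 / 0.90 = 400. Both figures reproduce. The 2.2 is the half-width for one overall mean and does not apply to a difference between frailty classes.

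**Spurious PF contrast, pooled classes.** The documents give neither frailty prevalence by age nor an age gradient in PF change. Assumptions:

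- three equal age strata, indexed 0, 1, 2;
- pre-frail or frail share of 15%, 25% and 45%;
- no true frailty effect;
- PF change differing by 1, 2 or 4 points per stratum.

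Mean age index:

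- pre-frail or frail: (0×15 + 1×25 + 2×45) / 85 = 1.353
- non-frail: (0×85 + 1×75 + 2×55) / 215 = 0.860
- gap: 0.49

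Raw contrast = slope × gap = 0.49, 0.98 and 1.97 points, or about 0.5, 1.0 and 2.0.

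**Precision of that contrast.** The pooled share is 85/300 = 28.3%, so 102 against 258 of 360. Half-width = 1.96 × 21.2 × √(1/102 + 1/258) = 4.9 points.

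**Frail class alone.** A second set of assumptions uses 120 evaluable subjects per stratum and slopes of 1 to 3 points. Frail shares run from 5/8/12% (non-frail 70/60/50%) to 1/7/27% (non-frail 85/55/25%).

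- Weak link: index gap 32/25 − 160/180 = 0.39; with slope 1, 0.4 points.
- Strong link: index gap 61/35 − 105/165 = 1.11; with slope 3, 3.3 points.

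The half-width with 30 to 42 Frail subjects is about 7 to 8 points. With age strata in the model the expected spurious difference is 0. The standard error rises from 4.13 to 4.16 (weak link), 3.71 to 3.88 (moderate) or 3.64 to 4.07 (strong).

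**Any solicited symptom.** With the same Frail shares, and rates assumed to fall by 5 to 15 percentage points per stratum, the spurious Frail minus Non-Frail difference runs from −5 × 0.39 = −2 to −15 × 1.11 = −17 percentage points.

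**Grade 3.** With assumed rates of 6%, 4% and 2% by stratum and the 15/25/45% shares:

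- pre-frail or frail: (15×6 + 25×4 + 45×2) / 85 = 3.3%
- non-frail: (85×6 + 75×4 + 55×2) / 215 = 4.3%

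The 1.0-point gap compares with a half-width of about 4.3 points. The mean rate of 4% gives about 14 events in 360. A model with age (2 parameters), frailty (2) and gender (1) would have about 3 events per parameter.

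**The case against.** The case for leaving the plan alone has real content.

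- **Status of the aim.** Frailty is in no objective or endpoint. The sub-analysis is conditional on the data, and Protocol 10.7 keeps all analyses descriptive. Part of the stated reason is to characterise the population, which one-way tables do. This stands and limits the weight of the point, but the protocol still asks about influence.
- **Partial cover.** The QALY model already gives one age-adjusted frailty estimate. SAP 6.1 tabulates demographics by frailty status, so the age mix of each class will be visible. Seeing the imbalance does not adjust PF change for it.
- **Reading of SAP 6.6.** Its wording could mean a cross-tabulation, the sentence in SAP 9 sits in a bullet that opens with pIMDs, and the table annex is not available. Separate splits are the more natural reading given Table 1, but for safety this is an inference. Crossed safety tables would still leave PF change unadjusted.
- **Legitimate description.** How frail vaccinees fare, unadjusted, is useful to vaccinators. That is a reason to keep the one-way rows, with adjusted results beside them.

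A reader might go further and infer that the primary result is biased, or that a spurious contrast near 2 points is serious because it approaches the planned precision of 2.2. Neither follows. The primary estimate is the overall within-subject change, which no frailty split touches. The right comparator for the pooled contrast is its own half-width of about 4.9 points.

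**Conclusion.** The point holds in limited scope. The available plan states a question about frailty and gives an age-adjusted answer for QALY loss but not for PF change or, apparently, for solicited symptoms. Confounding with age is likely, given the age-dependent content of the index and the even age quotas.

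Its size and direction cannot be taken from the documents. Under the assumptions above, the pooled PF contrast would be shifted by 0.5 to 2.0 points, less than its own sampling uncertainty. A shift of that kind would still displace the estimate and could be misread as a frailty effect. The sample size, the overall primary estimate and the QALY frailty estimate are not affected.

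Age adjustment would not settle everything. The SF-36 PF score is item 36 of the frailty index (SAP Appendix A), so the frailty classes overlap with baseline PF whatever is done about age.

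**What to change.** - **SAP 6.2.1.** Fit the model already coded in SAP 7.1.3.4 to PF change after each dose (`pf_change = agecat frail gender`). Report the frailty differences with 95% CIs beside the one-way rows. Pool Pre-Frail and Frail if Frail is sparse. Base any statement about frailty and PF on this model.
- **SAP 6.6.** For any solicited symptom only, add age-standardised rates by frailty class or frailty-by-age rows. Keep Grade 3 as a descriptive table labelled as unadjusted for age, because events are too few for a model.
- **Interpretation.** State that age adjustment does not remove the overlap from PF being item 36 of the index.

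The cost is a few sentences, reuse of existing code and a small number of extra tables, with no new data. The downside is a slightly wider interval and a possibly unstable fit if few subjects are Frail.
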